### **9.5 Isatuximab Interference with Indirect Antiglobulin Test Results**

Based on information published in relation to a drug of the same class as isatuximab, daratumumab[48], the CD38 protein is weakly expressed on the surface of red blood cells. Because of this, anti-CD38 antibodies in patients' plasma can lead to pan-reactivity and thus interfere with various blood bank serologic tests. For example, plasma samples from daratumumab-treated patients showed positive reactions in indirect antiglobulin tests, antibody detection (screening) tests, antibody identification panels, and antihuman globulin crossmatches. ABO/RhD typing is not affected by anti-CD38 antibody.

To avoid potential problems with blood transfusion, the American Association of Blood Banks recommends that patients being treated with anti-CD38 antibodies have blood type and screen tests performed at baseline. After treatment, and each time before blood transfusion, the antibody screen test (indirect Coombs test) should be performed.

### **9.6 Evaluation of Body Composition**

Fat and lean mass will be measured using DXA (Hologic QDR 4500, Hologic Inc., Waltham, MA) at the three pre-specified time points. Total lean mass, extremity lean mass, total fat and trunk fat mass, as well as visceral adipose tissue mass will be quantified using Hologic APEX 3.1 software (Hologic).

### **9.7 Patient-Reported Outcomes**

The European Organisation for Research and Treatment of Cancer (EORTC) QLQ-C30 includes 30 items resulting in 5 functional scales (physical functioning, role functioning, emotional functioning, cognitive functioning, and social functioning), 1 global health status scale, 3 symptom scales (fatigue, nausea and vomiting, and pain), and 6 single items (dyspnea, insomnia, appetite loss, constipation, diarrhea, and financial difficulties). Administration time is approximately 11 minutes.

The EORTC QLQ-MY20 is a disease-specific validated instrument, that contains 20 questions that measures 4 myeloma-specific PRO domains: disease symptoms, side effects of treatment, future perspective, and body image.

## **10. DATA REPORTING**

### **10.1.1 Method**

The DF/HCC Office of Data Quality (ODQ) will collect, manage, and perform quality checks on the data for this study.

### **10.1.2 Responsibility for Data Submission**

All participating sites are responsible for submitting data and/or data forms to the ODQ according to the schedule set by the ODQ.

## **11.0 DATA SAFETY MONITORING**

The DF/HCC Data and Safety Monitoring Committee (DSMC) will review and monitor toxicity and accrual data from this study. The committee is composed of medical oncologists, research nurses, pharmacists and biostatisticians with direct experience in cancer clinical research. Information that raises any questions about participant safety will be addressed with the Overall PI and study team.

The DSMC will review each protocol up to four times a year with the frequency determined by the outcome of previous reviews. Information to be provided to the committee may include: up-to-date participant accrual; current dose level information; dose-limiting toxicity (DLT) information; all grade 2 or higher unexpected adverse events that have been reported; summary of all deaths occurring within 30 days of intervention for Phase I or II protocols; for gene therapy protocols, summary of all deaths while being treated and during active follow-up; any response information; audit results, and a summary provided by the study team. Other information (e.g. scans, laboratory values) will be provided upon request.

## **12.0 STATISTICAL CONSIDERATIONS**

### **12.1 Study Design/Endpoints**

50 patients will be enrolled.

#### Statistical Power Calculations:

The reference CR rate after 4 cycles of treatment is assumed to be 0.27. A study with a sample size of 50 achieves 80% power to detect a difference (P1-P0) of 0.16 using a one-sided, one sample exact binomial test at a significance level of 0.10, assuming that the CR rate (P1) in the study population is at least 0.43. If 19 or more patients experience a CR, the study will reject the reference rate of 0.27 in favor of a higher CR rate. If 10% of patients do not complete 4 cycles of treatment, the sample size of 45 evaluable patients still achieves 80% power to detect a difference of 0.16 based on the above assumptions. With 45 evaluable patients, the study will reject the reference CR rate of 0.27 in favor of a higher rate if 17 or more patients experience a CR.

Primary Analysis: Efficacy analysis will be performed both the Intent-to-Treat (ITT) Population and Efficacy Evaluable (EE) Population. The ITT Population will include all treated patients, and the EE Population will include all patients who meet eligibility criteria, receive at least 1 cycle of study drug, and have at least 1 post-baseline efficacy assessment. The primary analysis will be based on the EE population, and will use the Investigator-assessed response data

evaluated according to consensus recommendations based on the IMWG criteria. CR (CR+sCR) rate to treatment after 4 cycles of KRDI as assessed by site Investigators using the International Myeloma Working Group (IMWG) Uniform Response criteria will be reported with 90% confidence interval. Secondary analyses will evaluate CR rate at other pre-determined time-points.

Secondary Analysis: Secondary analyses will evaluate overall response rate, MRD rate, PFS and OS. Overall response rate will be percent of patients who achieve at least partial response (PR). Percent of patients achieving MR or better will also be collected as clinical benefit response. MRD rate after 4 cycles, at completion of induction, and at 24 months will be determined by deep sequencing of genomic deoxyribonucleic acid from bone marrow samples using rearranged Ig locus-specific primers (Adaptive, Seattle, WA). PFS will be defined as the time from first dose of study treatment to the first documentation of PD or death from any cause during study. OS will be defined as the time from first dose of study treatment to death from any cause. For responders, time to response (TTR) and duration of response (DOR) will be analyzed. TTR will be defined as the time from first dose of study treatment to the first documentation of response (either PR, very good partial response (VGPR) or CR, nCR, and sCR). DOR will be defined as the time from the first PR, VGPR, or CR to the first documentation of PD or death, whichever occurs earlier.

Response rates together with confidence intervals (CIs) will be provided. Kaplan-Meier curves will be used to characterize the time-to-event outcomes (PFS, OS, response duration) when there is censoring; univariate summary statistics will be provided for TTR. In addition, outcomes including median PFS and median OS will be calculated within sub-groups based on risk status (standard vs high) and MRD status (positive vs negative).

A 90% CI for the response rate will be constructed for evaluating the efficacy of KRDI. Kaplan-Meier curves will be constructed to characterize PFS, OS, and DOR. One sample standard inferences for PFS, OS, and DOR will be made accordingly.

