## 5.2 Pre-Treatment Criteria

A new cycle of treatment may begin on the scheduled Day 1 of a new cycle if the following criteria are met within 24 hours of Day 1:

- ANC  $\geq 1,000/\text{mm}^3$  (growth factor support is permitted during cycles with the exception of Cycle 1 Day 1 (C1D1); it is allowed on the same day as treatment administration).
- Platelet count  $\geq 50,000/\text{mm}^3$  (platelet support is permitted during cycles of treatment; it is allowed on the same day as treatment administration, including C1D1).
- Any lenalidomide-related allergic reaction/hypersensitivity or sinus bradycardia/other cardiac arrhythmia AE that may have occurred has resolved to < Grade 1.
- Any other lenalidomide, carfilzomib, or isatuximab-related adverse event that may have occurred has resolved to <Grade 2.
- Herpes zoster lesions, if present, are dry.

If these conditions are not met on Day 1 of a new cycle, the subject will be evaluated weekly and a new cycle of therapy will not be initiated until the toxicity has resolved as described above. The maximum amount of time that treatment may be held for these toxicities to resolve is 3 weeks. If drug is held for more than 3 weeks due to toxicity, the patient is to discontinue all study treatment and enter the survival follow-up phase of the study.

For intra-cycle dosing on days where laboratory studies are scheduled, the following criteria must be met:

- Platelet count  $\geq 30,000$  (platelet transfusion support is permitted to meet criteria)
- Absolute neutrophil  $\geq 500/\text{mm}^3$  (growth factor support is permitted during cycles with the exception of Cycle 1 Day 1 (C1D1); it is allowed on the same day as treatment administration).

Intra-cycle dose modifications for all drugs will be allowed based on toxicity and according to dose modifications outline in Section 6.1, Table 9.

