### **Treatment Discontinuation**

Administration of isatuximab, carfilzomib, lenalidomide and dexamethasone can be discontinued permanently in the event of a treatment-related toxicity at the Treating Investigator's discretion.

If a delay of starting a new cycle is greater than 21 days, the subject should be discontinued from treatment, unless continuing treatment is mutually agreed upon by the Treating Investigator and the Lead Principal Investigator.

If isatuximab, carfilzomib, or lenalidomide requires permanent discontinuation before Cycle 4 induction, the subject's treatment will be discontinued at the end of Cycle 4 induction. If isatuximab, carfilzomib or lenalidomide requires permanent discontinuation during maintenance cycles, the subject may remain on study with the remaining drug(s). Dexamethasone may be discontinued without the subject discontinuing study treatment.

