## **9.0 MEASUREMENT OF EFFECT**

### **9.1 International Myeloma Working Group (IMWG) Response Categories**

Disease evaluations will be performed at the completion of each cycle of treatment during the induction phase and then at the completion of every even cycle (14, 16, 20, etc.) during maintenance phase until disease progression.

Isatuximab detection on serum immunofixation electrophoresis (IFE) has been demonstrated in patients treated and may interfere with the traditional IMWG criteria of negative serum IFE for CR or sCR. To mitigate this interference, serum M-protein interference sampling will be performed.

For all patients with VGPR, a positive serum IFE, and a negative M-protein by serum protein electrophoresis (SPEP), reflex IFE testing will be performed to confirm the presence of isatuximab on IFE. In addition, patients who have an SPEP of  $\leq 0.2$  g/dL and IgG kappa MM, reflex testing will also be performed to determine whether the para-protein identified on SPEP/IFE is monoclonal isatuximab or the patient's endogenous myeloma protein.

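### Section 12.1's 10% attrition scenario (45 evaluable, 17 CRs, 80% power) is built on 4-cycle completers, but the primary analysis uses the broader Efficacy Evaluable set

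*Combined protocol and SAP*

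**What the plan says.** All of the design text is in section 12.1. Fifty patients are enrolled, the reference CR rate is 0.27, and the test is a one-sided exact binomial at 0.10. With 50 patients the cut-off is 19 CRs and the stated power is 80%, "assuming that the CR rate (P1) in the study population is at least 0.43".

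The attrition scenario follows: "If 10% of patients do not complete 4 cycles of treatment, the sample size of 45 evaluable patients still achieves 80% power" under the same assumptions. Its decision rule is: "With 45 evaluable patients, the study will reject the reference CR rate of 0.27 in favor of a higher rate if 17 or more" patients reach CR.

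The next paragraph defines the analysis sets. ITT is all treated patients. EE patients must meet the eligibility criteria, "receive at least 1 cycle of study drug, and have at least 1 post-baseline efficacy assessment". Then: "The primary analysis will be based on the EE population". The endpoint is CR plus sCR after 4 cycles, assessed by the investigator.

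Three other places bear on who falls in EE:

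- Section 9.1: "Disease evaluations will be performed at the completion of each cycle of treatment during the induction phase".
- Section 5.2: "If drug is held for more than 3 weeks due to toxicity, the patient is to discontinue all study treatment".
- Section 6.1, Treatment Discontinuation: if isatuximab, carfilzomib or lenalidomide must be stopped permanently before cycle 4, the subject's "treatment will be discontinued at the end of Cycle 4 induction". The same paragraphs let treatment continue after a delay of more than 21 days if the treating and lead investigators agree.

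**The concern.** The word evaluable covers two different sets. In the power text a patient leaves the 45 by not completing 4 cycles. In the analysis text a patient who completes one cycle and has one assessment is in EE, whether or not cycle 4 is reached. Because disease is assessed after every induction cycle, someone who stops after cycle 1, 2 or 3 would normally have that one assessment and stay in the primary denominator.

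Two things follow. The planned number, cut-off and power under attrition do not belong to the analysis that decides the trial. And no rule says how an EE patient with no response documented after cycle 4 is scored. In a single-arm, open-label trial with investigator-assessed response, a result near the cut-off should not depend on how one word is read after the data are in.

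**Working it through.** **Inputs (section 12.1).** p0 = 0.27, p1 = 0.43, one-sided exact binomial, alpha 0.10, N = 50, 10% not completing 4 cycles (5 patients, leaving 45).

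**Formula.** For n patients analysed, the cut-off r is the smallest count with P(X ≥ r | n, 0.27) ≤ 0.10. Power is P(X ≥ r | n, 0.43).

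**Step 1: reproduce the plan.**

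- n = 50: P(X ≥ 18 | 0.27) = 0.103 is too large and P(X ≥ 19 | 0.27) = 0.059, so r = 19. Power is 0.804.
- n = 45: P(X ≥ 16 | 0.27) = 0.131 is too large and P(X ≥ 17 | 0.27) = 0.075, so r = 17. Power is 0.804.

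Both stated cut-offs and both stated powers are correct for the numbers given.

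**Step 2: vary the EE size.** Keep the plan's 5 non-completers, assume everyone is eligible, and let 0 to 5 of them meet the EE definition. The p column takes 17 CRs, all among completers. The last two columns are power under two readings of 0.43:

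- Reading A: 0.43 is the CR rate in the whole EE set, so power = P(X ≥ r | n, 0.43).
- Reading B: 0.43 is the rate in the 45 completers, and retained non-completers are non-CR, so power = P(X ≥ r | 45, 0.43).

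| Non-completers kept | EE n | Cut-off r | p for 17 CRs | Power, A | Power, B |
|---|---|---|---|---|---|
| 0 | 45 | 17 | 0.075 | 80.4% | 80.4% |
| 1 | 46 | 17 | 0.090 | 83.6% | 80.4% |
| 2 | 47 | 18 | 0.107 | 78.7% | 70.9% |
| 3 | 48 | 18 | 0.126 | 82.0% | 70.9% |
| 4 | 49 | 18 | 0.147 | 84.9% | 70.9% |
| 5 | 50 | 19 | 0.169 | 80.4% | 59.8% |

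The same 17 CRs reject 0.27 in the first two rows and not in the other four. Eighteen CRs reject up to n = 49 (p = 0.088) but not at n = 50 (p = 0.103).

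**Step 3: between the readings.** With all 5 kept, each having CR probability q, and cut-off 19 of 50, power is 65.2% at q = 0.10, 70.2% at q = 0.20, 73.5% at q = 0.27 and 80.4% at q = 0.43.

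**Step 4: how often it could matter.** With 45 completers at exactly 0.43, P(17 CRs) = 0.095 and P(17 or 18 CRs) = 0.206. If none of the others reach CR, the verdict would differ between the completer set and EE in about 1 trial in 10 (2 to 4 kept) to 1 in 5 (all 5 kept).

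**Step 5: EE below 45.** EE also requires eligibility, so it could be smaller. At n = 44 the cut-off is 17 and power at an EE rate of 0.43 is 76.8%.

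**The case against.** The primary set is not in doubt. Section 12.1 names EE, defines it and plans an all-treated analysis beside it. A reader might infer that the primary denominator is unspecified; the text does not support that. What is misaligned is the attrition sentence and its decision rule.

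A reader might also infer that using 0.43 for both 50 and 45 patients commits the plan to a 43% CR rate among non-completers. It does not. The two sample sizes are alternative scenarios, and one rate can apply to the analysed set in each.

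The 17-of-45 rule is conditional on 45 evaluable patients, and the stated test already implies a cut-off at any other size. That stands, but it does not say that a completer count is the wrong n to enter. Since the endpoint is CR after 4 cycles, scoring a patient who never gets there as non-CR is the natural reading. That also stands, but it is not written down.

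The number of patients affected is unknown. A stop within cycle 1 falls outside EE, permanent discontinuation of one drug before cycle 4 need not create a non-completer, and section 6.1 allows continuation by agreement after a delay of more than 3 weeks. The 10% is itself only a planning scenario. Finally, the primary objective is to estimate the CR rate, reported with a 90% confidence interval, so the test is not the only output.

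**Conclusion.** The point holds as a mismatch of populations within section 12.1. The stated attrition number, cut-off and power describe 4-cycle completers, while the primary analysis keeps patients who stop after one cycle with one assessment. In the plan's own 10% scenario the cut-off for the primary set can be 17, 18 or 19, and a result of 17 CRs can fall on either side of it.

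The tempting stronger reading is that the trial really has about 60% power. The documents do not support that. The 59.8% needs three things together: 0.43 is the completer rate, all 5 non-completers stay in EE, and none reaches CR. None of these is stated. If 0.43 is the EE rate, power is 78.7% to 84.9% for 45 to 50 patients and the 80% broadly holds; it also holds (80.4%) under the completer reading if at most one non-completer is kept. The power figures for 45 or more assume that all completers are eligible. The 1-in-10 to 1-in-5 figures further assume exactly 5 non-completers, no CR among them, and a completer rate of exactly 0.43, whereas the plan says at least 0.43.

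Confidence is high for the mismatch and for the changing cut-off, but not for any particular loss of power. It should be fixed.

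**What to change.** In section 12.1:

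1. Make evaluable in the decision rule mean the EE population. Keep any completer analysis as supportive, because narrowing EE to completers would remove early failures from the denominator.
2. State that an EE patient without a documented CR or sCR after cycle 4 counts as non-CR.
3. Replace the fixed 17-of-45 sentence with a rule: reject 0.27 if the CR count reaches the smallest number with exact one-sided p of at most 0.10 at the actual EE size. For reference: 17 at 44 to 46, 18 at 47 to 49, 19 at 50.
4. State that 0.43 is the EE rate. If it is the completer rate, restate power under 10% non-completion as about 60% to 80%, depending on how many non-completers stay in EE. In either case note that ineligible patients could take EE below 45.

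The cost is wording only, with no added patients or procedures. The stated power may come out lower, and so may the reported CR rate: 17 CRs is 37.8% of 45 (17/45) but 34.0% of 50 (17/50).

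### The primary CR test is run on the Efficacy Evaluable set, which can drop treated patients who cannot be CRs; whenever it does, the CR proportion is biased upward relative to all treated patients

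*Combined protocol and SAP*

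**What the plan says.** Section 12.1 sets enrolment ("50 patients will be enrolled") and tests the CR plus sCR rate after four cycles with a "one-sided, one sample exact binomial test at a significance level of 0.10". The null is given as follows: "The reference CR rate after 4 cycles of treatment is assumed to be 0.27". The alternative is 0.43, and the null is rejected at 19 or more CRs in 50.

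The section then allows for dropout: "If 10% of patients do not complete 4 cycles of treatment, the sample size of 45 evaluable patients still achieves 80% power". For those 45 patients the rejection cut-off becomes 17.

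The Primary Analysis paragraph defines two sets. The ITT set is every treated patient. The EE set is limited to patients who are eligible, "receive at least 1 cycle of study drug, and have at least 1 post-baseline efficacy assessment". Efficacy is analysed in both, but "The primary analysis will be based on the EE population". No decision rule is attached to the ITT analysis, and Section 12.1 has no rule that counts a treated but unassessed patient as non-CR. Section 9.1 places the response evaluations at the end of each induction cycle.

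**The concern.** There is no control arm to undergo the same exclusions, so the observed proportion is compared directly with a fixed number. Two of the three EE conditions, receiving a cycle and having a post-baseline assessment, are settled only after treatment starts. A patient who dies, withdraws or stops for toxicity during cycle 1 may fail both, because the first response evaluation comes at the end of that cycle. Such a patient cannot be recorded as a CR after four cycles, so leaving the patient out shrinks the denominator and leaves the numerator unchanged.

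At stake is whether the 0.10 error rate holds for treated patients, and whether the headline CR rate describes everyone who received the regimen.

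A second problem sits beside it. The 45 patients in the dropout allowance are those who complete four cycles, whereas EE asks for one. A patient who stops in cycle 3 is in EE but not among the 45, so the 17/45 rule does not belong to the set named as primary.

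**Working it through.** **Inputs.** From Section 12.1: N = 50, null rate 0.27, alternative 0.43, one-sided exact alpha 0.10, cut-offs 19/50 and 17/45. Assumed, because the documents do not give them: 0.27 is a rate among all treated patients; all 50 are treated; k of them are excluded from EE and all k are non-CR. I show k = 0 to 5. The upper end borrows the plan's 10% non-completion figure, which is not an EE-exclusion figure.

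**Step 1: reproduce the plan.** X is the number of CRs, binomial.
- 19/50: P(X ≥ 19 | 50, 0.27) = 0.0590; power P(X ≥ 19 | 50, 0.43) = 0.804. A cut-off of 18 would give 0.1034, so 19 is the smallest valid cut-off.
- 17/45: P(X ≥ 17 | 45, 0.27) = 0.0753; power P(X ≥ 17 | 45, 0.43) = 0.804. A cut-off of 16 would give 0.1314, so 17 is the smallest valid cut-off.

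Both stated powers and both cut-offs reproduce.

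**Step 2: exclude k non-CR patients.** With an all-treated rate of 0.27, the rate in EE is 0.27 × 50 / (50 − k) = 13.5 / (50 − k). For each EE size I take the smallest cut-off c with P(X ≥ c | 50 − k, 0.27) ≤ 0.10. The plan does not state cut-offs for 46 to 49 patients. The false-positive rate is P(X ≥ c | 50 − k, 13.5/(50 − k)). The fifth column gives the same rule's error if the EE rate were truly 0.27, which isolates discreteness.

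| k | EE size | EE rate | cut-off | error, no selection | error, k non-CR excluded |
|---|---|---|---|---|---|
| 0 | 50 | 0.270 | 19 | 0.0590 | 0.0590 |
| 1 | 49 | 0.276 | 18 | 0.0875 | 0.1026 |
| 2 | 48 | 0.281 | 18 | 0.0732 | 0.1017 |
| 3 | 47 | 0.287 | 18 | 0.0605 | 0.1007 |
| 4 | 46 | 0.293 | 17 | 0.0904 | 0.1652 |
| 5 | 45 | 0.300 | 17 | 0.0753 | 0.1642 |

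For k = 1 the error rises by 0.1026 − 0.0590 = 0.0436. Of that, 0.0875 − 0.0590 = 0.0285 is discreteness and 0.1026 − 0.0875 = 0.0151 is selection. For k = 5 selection accounts for 0.1642 − 0.0753 = 0.0889.

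If exclusion is random with probability d, and excluded patients are again non-CR, the false-positive rate is 0.112 for d = 5% and 0.165 for d = 10%.

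**Step 3: the 17/45 rule.** Take 17 CRs among 50 treated, with five non-completers, none of them a CR.
- On 45: 17/45 = 37.8%, p = P(X ≥ 17 | 45, 0.27) = 0.075, reject.
- On 50: 17/50 = 34.0%, p = P(X ≥ 17 | 50, 0.27) = 0.169, do not reject.

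**Step 4: power if all treated patients are analysed at 19/50.**
- If 0.43 is the all-treated rate, power is 0.804.
- If 0.43 holds only among completers and 10% do not complete, the all-treated rate is 0.9 × 0.43 = 0.387 and P(X ≥ 19 | 50, 0.387) = 0.593. With exactly 45 completers, P(X ≥ 19 | 45, 0.43) = 0.598.

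**The case against.** A reader might infer that the test's error rate is inflated outright, and that the drop from 19/50 to 17/45 is the EE exclusion at work. The documents do not support either reading.

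- **The number excluded is unknown.** With none excluded there is no inflation, and with one to three the error is essentially the nominal 0.10. The rates near 0.165 need 8% to 10% of treated patients (4 or 5 of 50) to be lost from EE.
- **Non-completion is not EE exclusion.** With evaluations after every induction cycle, a patient who stops in cycles 2 to 4 normally stays in EE, in the denominator, without a CR.
- **0.059 is a flattering baseline.** It is low because 19/50 happens to be conservative; an unbiased 18/49 rule already gives 0.0875.
- **EE also removes ineligible treated patients,** who may or may not be CRs, so that part of the definition has no fixed direction of bias. The plan also does not say whether receiving a cycle means starting or completing it.
- **The basis of 0.27 is not stated.** If it came from evaluable patients under similar exclusions, comparing it with EE would be closer to like with like.
- **The gap would be visible.** An ITT efficacy analysis is planned, and Section 12.1 calls for an account of deaths and withdrawals among all who received drug.

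All of this limits the size of the problem. It does not remove the direction of bias for patients lost in cycle 1 or never assessed, nor the fact that the visible ITT result carries no decision rule.

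**Conclusion.** The concern holds in conditional form. Whenever EE drops treated patients who stop in cycle 1 or have no post-baseline assessment, the primary CR proportion is biased upward relative to all treated patients. Taking 0.27 as an all-treated rate and the excluded patients as non-CR, the practical effect on the error rate is negligible up to three exclusions and material at four or five, where about 0.165 replaces a nominal 0.10. How many exclusions will occur cannot be read from the documents.

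Independently of that count, the 17/45 rule rests on a definition of evaluable that does not match EE, and it takes non-completers out of the denominator. With 17 CRs and five non-completers who are not CRs, the decision depends on which denominator is used. The plan's power arithmetic is correct as stated; the fault lies in the set it is applied to.

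**What to change.** Make the already defined all-treated (ITT) set primary. State that any treated patient without a documented CR or sCR after cycle 4 counts as non-CR. Use 19/50 as the single decision rule, which has type I error 0.059 and power 0.80 if 0.43 is the all-treated rate. Drop the 17/45 rule. Report EE as a sensitivity analysis, and say whether receiving one cycle means starting or completing it.

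The change is to wording; the all-treated analysis is already planned and no extra enrolment is proposed. The cost is a less favourable power statement. The claim that 80% is kept under 10% dropout has to be replaced: power at 19/50 is about 0.59 if 0.43 holds only among completers and 10% do not complete. The plan should therefore also say which patients the 0.27 and the 0.43 refer to.

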95% CI a	(0.1% to 21.9%)	(12.6% to 51.1%)	(6.8% to 40.7%)	(9.4% to 45.1%)	(12.2% to 28.9%)
Minimal response (MR)	0	3 (12.5%)	3 (12.0%)	3 (12.0%)	9 (9.3%)
Stable disease (SD)	8 (34.8%)	5 (20.8%)	6 (24.0%)	12 (48.0%)	31 (32.0%)
Progressive disease (PD)	5 (21.7%)	3 (12.5%)	3 (12.0%)	3 (12.0%)	14 (14.4%)
Unconfirmed PD	4 (17.4%)	3 (12.5%)	2 (8.0%)	0	9 (9.3%)
Not evaluable	5 (21.7%)	3 (12.5%)	6 (24.0%)	1 (4.0%)	15 (15.5%)
Clinical benefit rate (≥MR)	1 (4.3%)	10 (41.7%)	8 (32.0%)	9 (36.0%)	28 (28.9%)
95% CI a	(0.1% to 21.9%)	(22.1% to 63.4%)	(14.9% to 53.5%)	(18.0% to 57.5%)	(20.1% to 39.0%)

Confidence Interval (CI) a estimated by Clopper-Pearson Exact method;

*Study TED14154 (monotherapy in RRMM; Part A)*

As of the cutoff date of 05 January 2018, Part A was completed. A total of 26 patients with RRMM were treated in Part A, 12 patients at 10 mg/kg QW/Q2W and 14 patients at 20 mg/kg QW/Q2W. The median age was 67.0 years (range: 53 to 81 years). The median time from initial MM diagnosis to first study treatment dose was 6 years (range: 1.6 to 13.5 years). The median number of lines was 5.0 (range: 2 to 13 lines). All patients received prior combined lenalidomide and bortezomib, 61.5% received prior pomalidomide, 57.7% received prior carfilzomib, and 38.5% received prior thalidomide. Overall, the median number of cycles was 4.5 (range: 1 to 22 cycles). The median number of cycles was 3.0 (range: 1 to 22 cycles) at 10 mg/kg QW/Q2W and 5.0 (range: 2 to 18 weeks) at 20 mg/kg QW/Q2W.

Overall, the ORR was 23.1%, including 3 (11.5%) patients with VGPR and 3 (11.5%) patients with PR (Table 3). The ORR was 25.0% and 21.4% at 10 and 20 mg/kg QW/Q2W, respectively. The CBR was 38.5% overall (33.3% and 42.9% at 10 and 20 mg/kg QW/Q2W, respectively).

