dexamethasone (RVD).[20, 21] Among patients treated at the maximum tolerated dose of lenalidomide 25 mg days 1-14, bortezomib 1.3 mg/m^2 IV days 1, 4, 8, 11, dexamethasone 20 mg day of and day after bortezomib on a 21-day cycle, the ORR rate was 100% with rates of VGPR or better seen in 74% patients. The Southwest Oncology Group (SWOG) study S0777 validated this triplet regimen, showing superior PFS, OS, and ORR with the triplet combination of RVD versus the doublet combination of Rd alone in patients with NDMM without intention for immediate autologous stem cell transplant (SCT).[22]

Lenalidomide (REVLIMID®) in combination with dexamethasone was approved by both U.S. Food and Drug Administration (FDA) and the European Commission for the treatment of adult patients with previously untreated multiple myeloma who are not eligible for transplant, on 18 February 2015 and 20 February 2015, respectively.

Complete and updated adverse events AEs are available in IB.

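### Does it matter that the 90% confidence intervals for the response rates have no stated method or sidedness?

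*Combined protocol and SAP*

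**What the plan says.** Section 12.1 specifies the primary test completely: an exact binomial test, one-sided, alpha 0.10, against a reference CR rate of 0.27. It converts the test into counts: "If 19 or more patients experience a CR, the study will reject the reference rate of 0.27", with 17 or more as the cut-off if 45 patients are evaluable. Under Primary Analysis it adds that the CR rate "will be reported with 90% confidence interval".

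Under Secondary Analysis it says "Response rates together with confidence intervals (CIs) will be provided", with no level, and later "A 90% CI for the response rate will be constructed for evaluating the efficacy of KRDI". That last sentence does not say whether it means the CR rate or the overall response rate (ORR).

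None of these sentences gives an interval method or sidedness. The only method named anywhere is in footnotes to tables of earlier isatuximab studies in section 2.2 ("estimated by Clopper-Pearson Exact method"), which do not govern this trial.

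**The concern.** Two things could go wrong with an unspecified interval.

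First, a trial that just reaches its cut-off rejects 0.27 by the count rule, yet may print a 90% interval that includes 0.27. At 19/50 this depends on the method chosen, so the method could be picked after the data are seen, or a reader could take the interval as contradicting the test.

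Second, if the response rate in the Secondary Analysis means ORR, values near 100% are conceivable. Section 2.4 reports for a newly diagnosed triplet that "the ORR rate was 100% with rates of VGPR or better seen in 74% patients". A Wald interval behaves badly there: it can run past 100% or collapse to zero width.

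At stake is whether the reported intervals can be reproduced and how they are read. The trial's conclusion and its power are not at stake.

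**Working it through.** **Inputs (section 12.1).** "The reference CR rate after 4 cycles of treatment is assumed to be 0.27"; power is computed "assuming that the CR rate (P1) in the study population is at least 0.43"; n = 50, or 45 after 10% non-completion; one-sided alpha 0.10; cut-offs 19 and 17.

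**Step 1: reproduce the design.** With X ~ Bin(n, p):

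- n = 50: P(X ≥ 19 | 0.27) = 0.0590 and P(X ≥ 18 | 0.27) = 0.1034, so 19 is the smallest count within 0.10. Power P(X ≥ 19 | 0.43) = 0.8037.
- n = 45: P(X ≥ 17 | 0.27) = 0.0753 and P(X ≥ 16 | 0.27) = 0.1314, so 17 is right. Power P(X ≥ 17 | 0.43) = 0.8039.

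The stated 80% power and both cut-offs hold.

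**Step 2: lower limits around the cut-offs.** The Clopper-Pearson lower limit L solves P(X ≥ x | n, L) = a, with a = 0.05 for a two-sided 90% interval and a = 0.10 for a one-sided 90% bound. Wald is p ± 1.645·√(p(1−p)/n). At 19/50 that gives 0.38 − 1.645·√(0.38·0.62/50) = 0.38 − 1.645·0.0686 = 0.267.

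| Count | Test rejects | Exact, two-sided | Wald | Jeffreys | Wilson | Exact, one-sided |
|---|---|---|---|---|---|---|
| 18/50 | no | 0.2472 | 0.2483 | 0.2561 | 0.2582 | 0.2688 |
| 19/50 | yes | 0.2651 | 0.2671 | 0.2741 | 0.2760 | 0.2872 |
| 20/50 | yes | 0.2831 | 0.2860 | 0.2922 | 0.2940 | 0.3058 |
| 17/45 | yes | 0.2569 | 0.2589 | 0.2669 | 0.2690 | 0.2800 |
| 18/45 | yes | 0.2768 | 0.2799 | 0.2869 | 0.2889 | 0.3005 |

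Among these counts the four two-sided methods disagree about 0.27 only at 19/50. At 17/45 all four contain it; at 20/50 and 18/45 all four exclude it. The one-sided exact bound agrees with the test in every row.

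**Step 3: why the two-sided interval and the test part company.** The two-sided exact interval excludes 0.27 only when the one-sided p-value is at or below 0.05; the test rejects at or below 0.10. The p-values at the cut-offs, 0.0590 and 0.0753, fall between the two. At 20/50 the p-value is 0.0590 − P(X = 19) = 0.0590 − 0.0277 = 0.0313, and test and interval agree again. The cause is tail area, so specifying Clopper-Pearson two-sided would not remove it.

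**Step 4: how often this arises.** P(X = 19 | n = 50) is 0.0893 at 0.43 and 0.0277 at 0.27. For evaluable sizes 40 to 50, taken at the smallest rejecting count, exact and Wald contain 0.27 at all 11 sizes. Wilson and Jeffreys exclude it only at 41, 44, 47 and 50. The smallest rejecting count itself has probability of about 8% to 11% at 0.43.

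**Step 5: ORR near 100%.** At 48/50 Wald gives 0.96 ± 1.645·0.0277 = 0.914 to 1.006, against exact 0.879 to 0.993. At 50/50 Wald has zero width; the exact lower limit is 0.05^(1/50) = 0.942. Coverage of the nominal 90% Wald interval at n = 50, for assumed true ORRs:

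| True ORR | 0.89 | 0.90 | 0.95 | 0.97 | 0.98 |
|---|---|---|---|---|---|
| Wald coverage | 90.5% | 86.4% | 91.1% | 76.5% | 63.3% |

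Among these assumed rates, the serious failures are at 0.97 and 0.98. For context, section 2.3 gives an ORR of 89.3% for weekly carfilzomib, lenalidomide and dexamethasone, in relapsed disease. The plan does not propose a Wald interval.

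**The case for a change.** The best case for acting is that the primary objective in section 1.1.1 is to estimate the CR rate, so the interval is a headline result. The plan never calls it descriptive, and the Secondary Analysis ties a 90% interval to evaluating efficacy. The exact test does not settle the interval either, since an exact interval may be one- or two-sided and the two differ at the cut-off. A sentence or two would close the gap at almost no cost.

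The factual part of this stands: method and sidedness are absent, and the rate meant in the Secondary Analysis is ambiguous. The consequence does not follow. No claim of success depends on an interval, so choosing one after the fact gains nothing, and any reader given the count and denominator can compute whichever interval they prefer. A 90% confidence interval is ordinarily read as two-sided, and exact inference is the only binomial method the plan names for this trial, so a two-sided exact interval is the natural default. The Wald argument needs three assumptions together: that Wald is used, that the ambiguous rate is ORR, and that the true ORR is about 97% or more. The 100% figure in section 2.4 comes from a different, bortezomib-based triplet.

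**Conclusion.** The concern does not call for a change. The omission is real, but it is a reporting detail that an analyst would fill sensibly. The decision rests on an exact one-sided test whose cut-offs, type I error (0.059 and 0.075) and power (80.4% at both sizes) are correct, and the interval plays no part in it. At the two planned sizes the choice among the four two-sided methods affects whether 0.27 is covered at a single count, 19/50, with probability 8.9% at a true rate of 0.43 and 2.8% at 0.27. The mismatch with the test at the cut-off comes from a 5% tail set against a 10% one-sided test. It would persist with a named two-sided exact interval, while the one-sided exact 90% bound (0.287 at 19/50, 0.280 at 17/45) agrees with the test.

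This conclusion assumes the count rule alone is used to judge the primary endpoint, as section 12.1 sets out, and that analysts do not use a Wald interval for rates close to 100%.
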